1 TRIAL OVERVIEW SAKK 41/13-ASPIRIN

SAKK 41/13-Aspirin. Adjuvant aspirin treatment in PIK3CA mutated colon cancer patients. A randomized, double-blinded, placebo-controlled, phase III trial.

Sponsor: Swiss Group for Clinical Cancer Research (SAKK)

Trial registry No.: Swiss National Clinical Trial Portal (SNCTP): SNCTP000001339

Cancer Clinical Trials Registry (ClinicalTrials.gov): NCT02467582

European Clinical Trials Database (EudraCT): 2015-001482-57

Coordinating investigator: [name]. med. [name], Spital STS AG Thun, Switzerland

TRIAL TYPE AND CATEGORISATION

Clinical trial with IMP (including placebo as comparator).

Aspirin is a medication with marketing authorization in Switzerland and EU as an analgesic, anti-inflammatory and antipyretic drug and, at low dose, for the prevention and treatment of cardiovascular and cerebrovascular diseases. In this trial, low dose aspirin (i.e. 100 mg) will be used daily during 3 years for the adjuvant treatment of colon cancer. According to the Swiss HRA and its corresponding ordinance KlinV/Oclin on clinical trials, this trial is classified as category B.

OBJECTIVE

The trial objective is to demonstrate a statistically significant and clinically relevant disease-free survival benefit in stage II and III PIK3CA mutated colon cancer patients taking daily adjuvant aspirin for maximum 3 years.

ENDPOINTS

Primary endpoint:

- Disease-free survival (DFS)

Secondary endpoints:

[figure not shown]
- Time to recurrence (TTR)
- Overall survival (OS)
- Cancer-specific survival (CSS)
- Adverse events (AEs)

Additional research questions:

Patient's tumor will be investigated for the identification of predictive and prognostic markers for the response to adjuvant therapy with aspirin and for the assessment of the biology of aspirin-mediated response.

TRIAL DESIGN

International, multicenter, randomized, double-blinded, placebo-controlled, phase III trial.

The concomitant use of adjuvant chemotherapy for stage III and high risk stage II colon cancer according to international treatment guidelines is allowed (chemotherapy regimens include intravenous 5-fluorouracil or oral capecitabine either alone or in combination with intravenous oxaliplatin).

SELECTION OF PATIENTS

Refer to section 6 for the full list of inclusion/exclusion criteria

- Histologically confirmed diagnosis of adenocarcinoma of the colon
- Stage II (pT3/T4 N0 cM0) or stage III (pTx pN+ cM0) disease
- Presence of predefined, activating PIK3CA mutation in exons 9 or 20
- Complete curative tumor resection (R0) within 14 weeks maximum before registration
- Adequate performance status (PS 0-2) and hematological values
- No multiple adenocarcinomas of the colon
- No rectal cancer
- No severe or uncontrolled cardiovascular disease
- No upper gastrointestinal bleeding within 12 months prior to registration; no bleeding disorder that is an absolute contraindication to the use of aspirin
- No regular intake of acetylsalicylic acid or other non-steroidal anti-inflammatory drugs (NSAIDs) or cyclooxygenase (COX)-2 inhibitors
- No systemic rheumatic diseases or degenerative disorders affecting the musculoskeletal system with a relevant risk of requiring treatment with NSAIDs in the future
- No concurrent treatment with other experimental drugs, no administration of concomitant drugs contraindicated for use with the trial drug (the concomitant use of adjuvant chemotherapy for

stage III and high risk stage II colon cancer according to international treatment guidelines is allowed)

TRIAL DURATION

Duration of accrual: Initially planned 3 years, actual duration until premature closure of the trial (see section 5) 4.5 years

Duration of trial therapy (per patient): maximum 3 years (or until recurrence, death or consent withdrawal)

Duration of the follow-up (per patient): at least 3 years (from the date of surgery)

Duration of trial (in total): 7.5 years

The trial may be stopped early based on the results of two interim efficacy analyses or if new scientific data become available which change assessment of risk/benefit.

TRIAL SCHEDULE

Trial activation: Q2 2016

First patient in: Q2 2016

Last patient in: Q2 2019 (initially planned); Q4 2020 (after premature closure)

Last patient last treatment: Q2 2022 (initially planned); Q2 2021 (after premature closure)

Last patient last visit: Q2 2029 (initially planned); Q4 2023 (planned after premature closure)

TRIAL PRODUCT

Aspirin® (acetylsalicylic acid) is a salicylate drug that has analgesic, anti-inflammatory, antipyretic and antiplatelet properties. Aspirin is part of a group of medications called non-steroidal anti-inflammatory drugs, but differs from most other NSAIDs in the mechanism of action.

The comparator used in this trial is placebo, and both, aspirin or placebo are taken orally once daily.

TRIAL TREATMENT

Patients with resected colon cancer stage II or stage III bearing somatic mutations in exon 9 or 20 of PIK3CA will be 2:1 randomized to daily adjuvant aspirin 100 mg versus placebo for a maximum of 3 years or until disease recurrence, patient death or withdrawal of consent, whichever occurs first. Patients will be followed up for at least 3 years from the date of surgery.

The intake of aspirin or placebo is independent of adjuvant chemotherapy, and does not impact on the indication to give (or not to give) adjuvant chemotherapy.

MEASUREMENTS AND PROCEDURES

Following complete resection of their primary tumor, potentially eligible stage II or stage III colon cancer patients will undergo PIK3CA testing. Mutation screening will be performed centrally in archived formalin-fixed paraffin-embedded (FFPE) tumor tissue. Baseline assessments before trial treatment include clinical examination and blood testing for safety parameters and tumor marker. The trial therapy consists in daily aspirin (100 mg) or placebo *per os*.

The schedule of assessments during trial treatment and in the follow-up phase is in line with the guidelines from the Swiss Association for Gastroenterology (SGG/SSG) and the European Society of Medical Oncology (ESMO) for the follow-up of patients with colon cancer. Clinical examinations and carcinoembryonic antigen (CEA) measurements are to be performed every 3 months during the first 2 years following surgery, thereafter every 6 months until year 5. Bleeding-related adverse events potentially related to trial medication are to be recorded throughout trial treatment. Colonoscopy will be performed at year 1 and 4 following surgery, whereas computer tomography (CT) of the chest and abdomen are to be performed once a year. From year 6 to 10, disease and

survival status will be collected yearly. After recurrence, only survival status will be recorded for up to 10 years from surgery.

STATISTICAL CONSIDERATIONS

The sample size is based on the primary endpoint disease-free survival (DFS). Using a type I error of 5%, a power of 80% and a randomization ratio of 2:1, 43 events will be needed to show superiority of the aspirin arm under the alternative hypothesis that the hazard ratio (HR) is 0.456 (corresponding to a 3-year DFS of 70% in the placebo arm and 85% in the aspirin arm assuming constant hazards). The sample size needed is 185 patients (123 in the aspirin arm, 62 in placebo arm); the number needed to screen is estimated to be 1850 patients. All efficacy endpoints will be analyzed based on the full analysis population. The treatment effect will be assessed using Cox regression models with the treatment arm as independent variable and the stratification factors as strata.

GCP STATEMENT

This study will be conducted in compliance with the protocol, the current version of the Declaration of Helsinki, the ICH/GCP as well as Swiss and European legal and regulatory requirements.

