4 TRIAL DESIGN

This is an international, multicenter, randomized, double-blinded, placebo-controlled, phase III trial.

Initial design was that following complete resection of their primary tumor, potentially eligible stage II or stage III colon cancer patients will undergo central PIK3CA testing. Patients with somatic mutations will be 2:1 randomized to daily aspirin 100 mg versus placebo for a maximum of 3 years or until disease recurrence, patient death or withdrawal of consent, whichever occurs first. Patients will be followed up for at least 3 years from the date of surgery. However, the trial was prematurely closed for accrual and treatment, as described in chapter 5.

The intake of aspirin or placebo is independent of adjuvant chemotherapy, and does not impact on the indication to give (or not to give) adjuvant chemotherapy.

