4.1 Methods of minimizing bias

4.1.1 Randomization and stratification

Patients are randomized in a 2:1 ratio to the aspirin or placebo arm using the minimization method with 80% allocation probability according to the stratification factors:

- Stage II versus stage III colon cancer
- Left versus right hemicolon
- PIK3CA mutation in exon 9 versus 20
- Country

A total of 185 patients (123 in the aspirin arm and 62 in the placebo group) were planned to be randomized.

Due to the premature closure for accrual of the trial, 113 patients were randomized.

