5 TRIAL DURATION AND TERMINATION

The inclusion of patients has started in Q2 2016 and was planned to stop after the inclusion of 185 patients, which was initially expected in Q2 2019. Assuming a PIK3CA mutation rate of 17% based

on previous reports [13, 22], and some patients not being randomized into the trial due to patient's wish and eligibility criteria, the planned number of patients to be screened was 1850.

The trial may have been stopped prematurely based on the results of two interim efficacy analyses (see section 15, Statistical Considerations). In addition, accrual may have been interrupted and/or the trial may be stopped early if new scientific data become available which substantially change the benefit/risk ratio.

End of trial treatment was expected for Q2 2022.

In Q4 2020, the sponsor decided (due to financial reasons) to prematurely stop the accrual of the trial and the trial treatment at the next planned visit of each patient. Last patient, last treatment took place in Q2 2021, with the minority of accrued patients having reached the 3 years of treatment.

All patients randomized in Swiss sites will be followed-up for at least 3 years from the date of surgery until the last patient reaches the 3 years. The follow-up of patients randomized in foreign sites was stopped in Q2 2021 (after last patient, last treatment). Trial termination (last patient, last visit) was initially foreseen for Q2 2029, but is now foreseen in Q4 2023.

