7.5 Unblinding procedures

Unblinding during the conduct of the trial should be restricted to the cases where there are compelling medical or safety reasons to do so.

If unblinding is considered for non-emergency cases, the local investigator should contact the SAKK CC and the coordinating investigator immediately. Any reasons for unblinding – except for an emergency case – have to be discussed beforehand with the coordinating investigator or the Medical Advisor of the SAKK CC.

For the case that emergency unblinding is necessary:

A scratch off card is provided to the site by the SAKK CC for each patient after the initial DCN allocation (at the start of trial treatment). SAKK CC ensures the correct attribution of a card to each patient by double signatures and documentation.

Sites are responsible to store the card in the investigator's file. In case an investigator breaks the code of a patient, the SAKK CC has to be informed immediately. The investigator will be instructed to keep the information strictly confidential.

Documentation of unblinding:

Any breaking of the code (intentional and unintentional) must be reported and explained via EDC in the CRF "Unblinding" (UB), irrespective of the reason for its occurrence. The unblinding and reason for unblinding must be recorded.

At the time when the trial treatment was prematurely stopped by the sponsor in December 2020 (see section 5), all participating sites received the information about the allocated treatment arm of their

specific patients in order to inform them about the treatment they had received. That allowed the patients to decide together with their treating investigator whether or not to continue aspirin treatment outside of the trial. Since this general unblinding process involved all patients randomized to the trial, with the same date and reason for all of them, it must not be documented on the CRF UB via EDC.

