15 STATISTICAL CONSIDERATIONS

15.1 Sample size estimation

- Software package: East 6.2
- Number of treatment arms: 2
- Type of design: parallel design
- Trial intention: superiority
- Statistical test: One-sided log-rank test
- Null hypothesis: hazard ratio (HR) 1.0
- Alternative hypothesis: HR 0.456 (corresponding to a 3-year DFS of 70% in the placebo arm and 85% in the aspirin arm assuming constant hazards). This hazard ratio is based on the two published retrospective studies: The hazard ratio for cancer-specific survival in the study by Liao et al. [13] was 0.18, the hazard ratio in the study by Domingo et al. [14] for recurrence was 0.11. Therefore, the assumed hazard ratio of 0.456 in this trial represents a conservative estimate. The assumption of a 3-year DFS of 70% in the placebo arm was based on several studies [4, 13, 14, 26] as well as analyses of the SEER data base (<http://seer.cancer.gov/data/>) and analyses performed on data of the Cantonal Hospital St. Gallen.
- Type I error: 5%
- Power: 80%
- Randomization ratio: 2:1
- Number of interim analyses for the primary endpoint: Two
- Timing of interim analyses: after 25% (11) and 50% (22) of the events, the first is expected after approximately 2.4 years of accrual and the second after approximately 0.5 years of follow-up.
- Stopping boundary for benefit/futility: Lan-DeMets error spending function in spirit of the O'Brien & Fleming boundary [27, 28].
- Expected accrual rate: 60 patients per year
- Expected accrual time: 3 years
- Expected follow-up time until primary analysis: 3 years
- Expected proportion of lost to follow-up: 20%. This is based on various studies assessing aspirin intake [29-31].
- Required number of events: 43
- Sample size: 185 (123 in the aspirin group, 62 in placebo group)

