15.3 Statistical analyses

The primary analysis will take place once the 43rd DFS event has taken place or at the latest after 3 years from the date of surgery of the last included patient.

All efficacy endpoints will be analyzed based on the full analysis population. Supportive analyses based on the PP population will be performed. All safety endpoints will be analyzed based on the safety population. Subgroup analyses for all stratification factors except country are planned for the primary endpoint. All time-to-event endpoints shall have the median value of each treatment group estimated using the Kaplan-Meier method, along with a 95% confidence interval. The number of events of each endpoint shall be presented descriptively by frequency and percentage by treatment arm. The treatment effect will be assessed using Cox regression models with the treatment arm as independent variable and the stratification factors as strata. Cox regression models will also be used to investigate the potential effects of other factors (e.g. chemotherapy given and concomitant therapy) on selected endpoints. Subgroup analyses may be performed for these factors. For the primary analysis, patients who were unblinded before experiencing an event will be censored at the date of the last available tumor assessment before unblinding. A supportive analysis will be performed in which the unblinding will not be considered.

Categorical variables will be summarized with frequency and percentage and may be compared between arms by chi-square tests or Fisher's exact tests. Continuous variables will be summarized using median and range and may be compared between arms by t-tests or Wilcoxon rank sum tests.

Laboratory values will be expressed as the absolute values and as grading according to NCI CTCAE v4.0 by treatment arm. AE grading shall be presented by type, grade, and relation showing frequency and percentage of the within-patient worst grades by treatment arms. In addition, grade ≥ 3 AEs and AEs with relation to treatment ≥ 3 will be summarized separately.

Full analysis details will be outlined in the statistical analysis plan (SAP).

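### The overview and section 15.1 still state 80% power from 43 events in 185 patients, but the closed trial of 113 patients can expect about 36 events at best, and about 16 to 18 if the unblinding censoring applies

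*Combined protocol and SAP*

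**What the plan says.** The statistical paragraph of the overview reads: "Using a type I error of 5%, a power of 80% and a randomization ratio of 2:1, 43 events will be needed", for a hazard ratio (HR) of 0.456 and 185 patients. Section 15.1 gives the same design (one-sided log-rank test, 5%, 80% power, 2:1, "Required number of events: 43") and lists "Expected proportion of lost to follow-up: 20" per cent. Neither place marks these figures as superseded.

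Other sections were updated. Section 4 opens its description with "Initial design was that following complete resection of their primary tumor". Section 4.1.1 says that 185 patients had been planned and then: "Due to the premature closure for accrual of the trial, 113 patients were randomized". Section 5 reports the early stop of accrual and treatment, and adds: "The follow-up of patients randomized in foreign sites was stopped in Q2 2021".

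Section 15.3 sets the primary analysis at the 43rd event or, at the latest, three years after the last patient's surgery. It says of the primary analysis that "patients who were unblinded before experiencing an event will be censored at the date of the last available tumor assessment before unblinding", with a supportive analysis that ignores unblinding. Section 7.5 describes the December 2020 release of treatment codes to all sites: "Since this general unblinding process involved all patients randomized to the trial".

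The end of follow-up has two dates. The overview schedule and section 5 give Q4 2023; section 12.3 gives Q3 2024.

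**The concern.** A reader of the overview or section 15.1 takes 80% as the power of the trial being analysed. With 113 patients instead of 185, and with part of the follow-up cut off, 43 events are unlikely by the calendar deadline. The deadline in section 15.3 permits an analysis with fewer events, but the plan does not say how many to expect.

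The unblinding rule makes this worse. Read literally, it censors every event-free patient at or before December 2020, so the primary analysis would hold about half the events of the supportive one. A non-significant result would then be judged against a power that the trial does not have.

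**Working it through.** **Inputs from the plan.** 3-year DFS 70% and 85% with constant hazards, one-sided 5%, 2:1, 20% loss (section 15.1). 113 randomized (section 4.1.1). Accrual Q2 2016 to Q4 2020, follow-up to Q4 2023 (overview). Foreign follow-up to Q2 2021 (section 5). Unblinding in December 2020 (section 7.5). Alternative end date Q3 2024 (section 12.3).

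**Assumptions not in the documents.** Uniform accrual; loss exponential, reaching 20% at 3 years; mid-quarter dates; Swiss share varied; the full HR persisting after treatment stopped. Time at risk runs from entry.

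**Formulas.**
- Hazards per year: placebo −ln(0.70)/3 = 0.1189; aspirin −ln(0.85)/3 = 0.0542; ratio 0.456.
- Loss rate η = 0 or −ln(0.8)/3 = 0.0744.
- Event probability for follow-up T: λ/(λ+η) × [1 − exp(−(λ+η)T)], averaged over entry dates.
- Power = Φ(√(d·f) × 0.785 − 1.645), where d is the number of events and 0.785 = |ln 0.456|. The factor f is 2/9 (allocation) or p(1−p), with p the aspirin share of events expected under the alternative (f ≈ 0.25).

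**The plan's own figure.** At d = 43:
- f = 2/9: Φ(3.091 × 0.785 − 1.645) = 78.3%.
- f = 0.25: Φ(3.279 × 0.785 − 1.645) = 82.4%.
- 185 patients at 60 per year plus 3 years, with 20% loss, give 44.7 expected events.
- O'Brien-Fleming-type spending at 11, 22 and 43 events gives z = 3.70, 2.51, 1.66. With f = 0.25 the interim HR bounds are 0.107 and 0.343, against 0.11 and 0.34 in section 15.2; with 2/9 they are 0.094 and 0.322.

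The original design therefore reproduces, and f ≈ 0.25 matches its interim bounds.

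**113 patients to Q4 2023, no loss, all followed.** Follow-up is spread evenly over 3 to 7.5 years.
- Aspirin: 1 − (0.850 − 0.666)/(4.5 × 0.0542) = 0.246; × 75.3 patients = 18.5 events.
- Placebo: 1 − (0.700 − 0.410)/(4.5 × 0.1189) = 0.458; × 37.7 patients = 17.2 events.
- Total 35.8, so power is 71.5% (2/9) or 75.8% (f ≈ 0.25). A simulated log-rank test gives about 75%.

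**All scenarios, uniform accrual:**

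| Cut-off and Swiss share | Events, no loss | Power | Events, 20% loss | Power |
|---|---|---|---|---|
| Q4 2023, 100% | 35.8 | 72-76% | 29.9 | 65-69% |
| Q4 2023, 80% | 32.7 | 68-73% | 27.5 | 62-66% |
| Q4 2023, 50% | 28.1 | 62-67% | 24.1 | 57-61% |
| Q3 2024, 100% | 39.8 | 75-80% | 32.5 | 68-72% |
| Censored at December 2020 | 17.6 | 46-50% | 15.8 | 43-47% |

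In each power range the first figure uses 2/9 and the second the split under the alternative.

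**Accrual shape.** Triangular accrual, all Swiss, no loss, Q4 2023 gives 31.6 (back-loaded) to 39.9 (front-loaded) events, 67-80% power. Censored at December 2020, the count ranges over about 11 to 23. Of the combinations tried, only front-loaded accrual, all Swiss, no loss and Q3 2024 together reach 43 (43.6 events). With uniform accrual and all patients Swiss, the 43rd event is expected about Q2 2025 without loss and about Q4 2028 with loss.

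**Dates.** Accrual closed in Q4 2020 and surgery precedes registration (criterion 6.1.6). Three years from the last patient's surgery therefore ends by 31 December 2023. Q3 2024 would require surgery in Q3 2021.

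**The case against.** The strongest reply is that the sentence is not false. It is conditional: given 5% and 80%, 43 events are needed. A sample-size section records planning inputs, and the shortfall can be inferred from sections 4.1.1, 5 and 15.3. This is correct as to the original calculation, which contains no arithmetic error. However, the sponsor labelled initial figures elsewhere and not here, and the calendar deadline supplies neither an event count nor a power.

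Second, compared within one convention the best-case loss is only about 6 to 7 points (78 to 72, or 82 to 76). That stands for the best case. It assumes no loss and no foreign patients, although section 5 says there were some.

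Third, the censoring rule may have been meant for individual code breaks only. Section 7.5 keeps the general unblinding off the unblinding form, and censoring everyone at December 2020 would leave the retained Swiss follow-up with nothing to add to the primary DFS analysis. This is a reasonable reading, but section 15.3 contains no such exemption. The 43-50% figure is therefore conditional on the literal reading.

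Finally, section 15.3 defers full details to an analysis plan. The text available for this review contains no restated power there; if one exists, the two protocol sections should point to it.

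**Conclusion.** The concern holds. The 43-event, 185-patient, 80% statement is sound for the original design but stands as current, unlabelled text for a trial that closed at 113.

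The size depends on the analysis. If unblinding is ignored, the shortfall is moderate: at most about 36 events and 72-76% power at Q4 2023 under uniform accrual, falling to 24-33 events and 57-73% over assumed Swiss shares of 50-80% and loss of 0-20%. If the primary analysis censors at the general unblinding, the shortfall is large: about 16-18 events and 43-50% power.

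The about-36 ceiling belongs to uniform accrual; front-loading would raise it to about 40. The conflicting end dates move the latest analysis date by up to three quarters, and only Q4 2023 fits the accrual closure.

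**What to change.** - In the overview and section 15.1, label 43 events, 185 patients and 80% power as the original design.
- Beside them, state the expected events and power for the 113 randomized patients, using the actual entry dates and Swiss share, which the sponsor knows. An expected confidence-interval width would serve equally well, if it is for a 90% two-sided interval so that it matches the one-sided 5% test.
- Give these figures separately for the primary analysis with unblinding censoring and for the supportive analysis without it. State in section 15.3 whether the rule covers the December 2020 unblinding.
- Reconcile Q4 2023 (overview, section 5) with Q3 2024 (section 12.3).

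The cost is text only. No patients are added and no endpoint or population changes. The price is a less favourable stated power.
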